Three key deliverables from this project will be: 1) empirical data on study feasibility (recruitment flow, training participation, and loss to follow-up); 2) a mixed methods evaluation of the acceptability of PsychArmor S.A.V.E.; and 3) measurement characteristics of key outcome variables for use in design of larger-scale RCT. If successful, this project will seamlessly link outreach via social media outreach to an online training in suicide prevention skills. This line of research has major potential for implementation and impact due to its broad reach and scalability.

Hypothesis:

This study has three hypotheses related to Aim 1:

- **Hypothesis 1.1:** Twenty participants per week, on average, will enroll in the study
- **Hypothesis 1.2:** At least 50% of eligible individuals will enroll in the study
- **Hypothesis 1.3:** Loss to follow-up at the study endpoint will be less than 50%

And one hypothesis related to Aim 2:

- **Hypothesis 2:** Participants will complete on average at least 70% of the PsychArmor S.A.V.E. training.

Scientific Rationale and Significance

Suicide prevention among Veterans not engaged in Veterans Health Administration (VHA) care and Veterans transitioning from military service is an urgent priority. An estimated 70% of Veterans who die by suicide have not recently used any VHA services.¹ The latest data further show that suicide rate among Veterans who do not use VHA care increased by 12% between 2016 and 2017.¹ As a consequence, addressing lack of help-seeking has been called one of the top three short-term research objectives in suicidology.² Addressing this barrier is especially critical among young Veterans transitioning from military service to civilian life who may face disruption in their social networks and challenges establishing care with VHA.

Veterans' close supports—which includes include family members and friends, as well as Veteran peers—have a vital role to play in increasing help-seeking and treatment engagement among Veterans at risk of suicide. Support and encouragement from Veterans' close supports is a key facilitator of help-seeking.³ In addition, suicidal individuals are most likely disclose their thoughts to a close social network member.⁴ Individuals having frequent social contact with at-risk individuals have the greatest potential to impact suicide prevention.⁵

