A subset of approximately 15 participants from the intervention group will be invited to participate in an interview. These participants may be veterans or their close supports. For this, a research staff member will contact potential participants to determine interest and conduct the interview in a format (telephone, video call, or in-person) that is best suited to each research participant.

Intervention Description. We will use PsychArmor S.A.V.E. (see description above in Scientific Rationale and Significance section). In brief, the online training is tailored to Veterans and their close supports, is free, brief (24 minutes), and includes three scripted role plays. It closely follows the S.A.V.E. model employed by the VA by teaching four skills: learning Signs of suicide, Asking about suicidal thoughts, Validating feelings, Encouraging help and Expediting treatment.⁵⁰

Control Group Description. Consistent with best practices for behavioral interventions, our control group accounts for the benefits seen with the passage of time and attention received in the intervention group.⁵¹ The control group will consist of a “sham” training – a different online, video-based training course developed by PsychArmor Institute designed for transitioning military service members and their family. Topics in this training include information on preparing finances, networking, searching for a job, and using educational benefits. The length of the training will be matched to the intervention (24 minutes), and the “sham” training also contains other design features similar to the intervention (e.g., motion graphics). By using another PsychArmor training, we are able to isolate the difference seen in the control group to be the educational content related to S.A.V.E.

Sources of Data. We will use three data sources (website administrative data, survey responses, and qualitative interviews) to obtain a mixed methods evaluation of PsychArmor S.A.V.E.

1. **Website administrative data.** These include measures of engagement with the web-based training in the current study: number of log-ins, enrollments, and completed trainings, as well as time spent on the website. These data will only be obtained from participants who are enrolled in the study.

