Given the 6-month length of follow-up, another potential difficulty is sample retention. To promote sample retention we will employ methods with empirical validation in increasing online study response and retention rates: 1) minimizing survey burden, 2) specifying survey time estimates, and 4) sending reminder emails, texts, and small messages of appreciation to study participants.⁵³ Of note, prior research among military personnel suggests that survey retention is higher in web-based surveys than paper-based surveys.⁵⁴ We will also employ modest financial incentives. In the case of incomplete follow-up, reminders will be sent with use of email and additional modalities (e.g., text message) as consented to by the participant.

Timetable for study. The project timeline is presented in the **Table 1**. Special consideration was made for the time required to: develop the social media ad campaign (3 months), setup study infrastructure including REDCap data collection and management system and a study website containing integration of the two study arms (4 months), and conduct recruitment (2.5 months) and participant follow-up (6 months). During the dissemination and next steps phase, we will prepare a grant application for the larger-scale RCT and prepare the study products noted above.

Activity	Table 1		Year 1		Year 2			
	Quarter		Q 1	Q 2	Q 3	Q 4	Q 1	Q 2
Start-up, IRB, and hiring	X							
Social media ad development		X						
Study infrastructure setup		X	X					
Online recruitment			X					
Baseline & follow-up assessments					X	X		
Interview training			X					
Interview conduct				X				
Qualitative data analyses						X	X	
Quantitative data analyses						X	X	
Dissemination/Next steps							X	

Measures. A timeline of measures is presented in **Table 2** and described further below.

Table 2: Summary of Study Measures

Timepoint(s)	Measure	Main Function	Aim(s)
0	Numbers screened, eligible, and enrolled per week; proportion eligible who enroll	Feasibility	1

PT, 1, 2, 3, 4, 5, 6	Retention rate; survey completion rate; exposure	Feasibility	1
PT	Completion of training; satisfaction; usability	Acceptability	2
0	Background characteristics	Descriptive data	1, 2
0, PT, 2, 4, 6	Intention to use of gatekeeper behaviors	Mechanisms of action	2
0, PT, 2, 4, 6	Knowledge; stigma; self-efficacy; social norms	Mechanisms of action	2
0, PT, 1, 2, 3, 4, 5, 6	Gatekeeper behaviors; suicidal ideation; help-seeking, social support	Measurement characteristics	2

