1	Semi-structured interview about social media ads and PsychArmor S.A.V.E.	Feasibility and acceptability	1, 2

0=pre-training (baseline); PT=post-training (immediately after); 1=1-month follow-up, 2=2-month follow-up, etc.

Feasibility: We have selected feasibility measures most appropriate for a pilot intervention and previously used to assess online interventions.^{55, 56} These measures address each stage of the project including screening (number screened/eligible per week), recruitment (number enrolled per week), randomization (proportion of eligible who enroll), cross-contamination (number of control group participants who report taking PsychArmor S.A.V.E. training), retention (i.e., loss to follow-up), and assessment process (survey completion rates).

Acceptability: For acceptability, we will use a combination of three measures: completion of the training, satisfaction (measured using the validated eight-item Client Satisfaction Questionnaire (CSQ-8),⁵⁷ and the System Usability Scale (SUS) along with a single item usability rating that is highly correlated ($r=0.82$) with the SUS.^{58, 59}

Background Characteristics: This will include standard items on age, gender, race/ethnicity, education, marital status, zip code (rurality), occupation, military experiences, social media platform use, frequency of social contact with Veterans, social network size, and VA and other health service use.

Intentions to Use Gatekeeper Behaviors: Suicide prevention training research has shown that behavioral intention has a direct effect on actual behavior and also mediates the relationship between attitudes and actual behaviors.⁶⁰ Thus, we have chosen a three-item scale to assess behavioral intentions to use core skills learned in gatekeeper training (recognizing gatekeeper opportunities, inquiring about suicidal ideation, and making a professional referral). In research conducted by our research team and others, scales of intentions to use gatekeeper behaviors have shown adequate internal reliability.^{14, 60}

Knowledge: The 12-item short form of the Literacy of Suicide Scale (LOSS) measures knowledge about suicide. A total literacy score can be calculated as the percent of all correct items.⁶¹

Stigma: The 16-item short form of the Stigma of Suicide Scale (SOSS) measures public stigma towards individuals who die by suicide. It shows reliability and validity in community-based samples.⁶²

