Randomization and Blinding. Block-randomization schemes using random block sizes to assign the two study arms will be created in R using the blockrand package (Version 1.3) before study start and pre-loaded into REDCap. Following recommendations for blinding in behavioral interventions, participants will be blinded by limiting details about the study hypotheses and differences between the study arms.⁶⁹ Blinding will also be achieved because no study personnel are involved in intervention delivery, and the biostatistician will be blinded for analyses involving study group comparisons.

Statistical Analyses. We will examine descriptive statistics and distributions for variables at each of their timepoints. Variables will be summarized both with the arms combined and stratified. Differences in baseline values between study arms will be tested using t-tests or chi-squared tests. For variables measured with multiple items, Cronbach's alpha will be conducted to examine internal reliability, and, when necessary, measurement modifications will be made to improve reliability. If missing data meet minimal missing data assumptions (i.e., at least missing at random), then multiple imputation or full maximum likelihood estimation can be used to improve standard errors compared with analyses based on listwise deletion.⁷⁷ All statistical analyses will be done in R.

Qualitative Interview Sample Considerations. A small subgroup of study participants (n = 15) who were assigned to the intervention group will be invited to participate in an interview to take place approximately one-month post-intervention. We will use maximum variation sampling, a purposive sampling strategy which increases depth of understanding by selecting a diverse group of individuals who are expected to communicate different perspectives.⁷⁰ Characteristics considered in sampling will be use of gatekeeper behaviors, transitioning Veteran vs. close support, rurality, and VHA service use.

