If any AEs or UPs require a change to the protocol or consent form (as determined by the PI or IRB) the PI will submit the revised protocol for review and approval by the Joint IRB promptly. A brief summary of UPs and all adverse events will be submitted to the IRB at the time of annual continuing review. Adverse events, enrollment, and data collection problems will be reviewed quarterly by the PI. In addition, dropouts and AEs will be reviewed for patterns indicating problems with the study procedures. Any protocol deviation identified during the quarterly reviews will be reported per IRB policy.

Step-by-Step Guidance on Conducting the Study

1. Project Setup
 - 1.1. Social media campaign (**Appendix E**) development
 - 1.1.1. [name] to deliver workshop to develop messages for ad campaign
 - 1.1.2. Consultation with OHSU Strategic Communications social media team and a Veteran engagement representative
 - 1.1.3. Submit finalized social media ads to IRB for approval
 - 1.2. REDCap setup
 - 1.2.1. Build survey (**Appendix B**) in REDCap with consultation from Oregon Clinical and Translational Research Institute (OCTRI)
 - 1.2.2. Submit any substantive changes to survey to IRB for approval (if applicable)
2. Recruitment
 - 2.1. Implement social media ad campaign on Facebook
 - 2.1.1. Monitor recruitment pacing through REDCap
 - 2.2. Interested participants click on a link to connect to the study website on OHSU's REDCap
 - 2.3. Interested participants complete electronic eligibility screening
 - 2.4. Eligible participants will be directed to an information sheet (**Appendix A**) for electronic informed consent
 - 2.5. Consented participants provide contact information (name, phone number, email address) needed for follow-up (if participants choose to withdraw, they will be given the option to stop receiving communications of any format from the study team).
 - 2.6. Participants will be randomly assigned to either the intervention or control group trainings
3. Intervention
 - 3.1. Participants will complete the baseline survey (see table 2, reproduced below, for included measures)
 - 3.2. Participants will view either intervention gatekeeper training or control "sham" training
 - 3.2.1. Data collected on training completion rates

- 3.3. Participants will immediately complete a follow-up survey (see table 2 for included measures)
- 4. Longitudinal survey follow-up

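### Satisfaction and usability are asked once, right after the training, with no stated route for early stoppers, and interview sampling omits completion, so opinion data on acceptability will probably lean toward those who stayed

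*Combined protocol and SAP*

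**What the plan says.** The Acceptability paragraph under Measures states that "we will use a combination of three measures: completion of the training, satisfaction" and usability. Table 2 places all three in one row, "Completion of training; satisfaction; usability", with PT as the only timepoint, and its footnote defines the code: "PT=post-training (immediately after". The Step-by-Step Guidance runs in sequence: participants view a training (3.2), then "Participants will immediately complete a follow-up survey" (3.3). Neither place says what happens when a participant closes the training before the end.

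Completion has its own source. Sources of Data, item 1, lists "number of log-ins, enrollments, and completed trainings, as well as time spent on the website", and adds: "These data will only be obtained from participants who are enrolled in the study". It is also the only acceptability measure with a hypothesis and threshold: "Participants will complete on average at least 70% of the PsychArmor S.A.V.E. training".

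For the interviews, Qualitative Interview Sample Considerations plans maximum variation sampling of 15 people assigned to the intervention: "Characteristics considered in sampling will be use of gatekeeper behaviors, transitioning Veteran vs. close support, rurality, and VHA service use". How much of the training a person completed is not listed.

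**The concern.** Acceptability has a behavioural part (did people finish?) and an opinion part (CSQ-8, SUS and the interviews). The people whose opinions are most informative about what is wrong with a training are those who left it. For them, the plan has no step that obtains a rating and no sampling rule that secures an interview.

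Non-response here is unlikely to be random, since a person who stops because the training does not suit them plausibly would have scored it low. The only missing-data provision, in Statistical Analyses, is optional and is conditional on data being at least missing at random, which is the doubtful assumption for these scores.

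At stake is one of the project's three deliverables, the mixed methods evaluation of acceptability, and with it the guidance for the larger trial. Ratings that lean toward stayers would look better than the arm as a whole would have given, and the interviews might say little about why people stopped.

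**Working it through.** **1. The plan's own completion figure.** Sample Size Considerations assumes mean completion of 73%, SD 15%, n = 100. The t interval is 73 ± 1.984 × 15/√100 = 73 ± 2.98, or 70.02% to 75.98%. This reproduces the stated interval.

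**2. What that assumption implies about stopping early.** Treat the figure as percentage completed, capped at 100%. Reaching 100% means lying 27 points above the mean. The one-sided Chebyshev (Cantelli) bound on the share that can do so is SD²/(SD² + 27²) = 225/(225 + 729) = 23.6%. On the plan's own numbers, then, at least 76% of the arm would stop short of the end. The wider scenario in the same section (mean 76%, SD 25%) gives 625/(625 + 24²) = 625/1201 = 52%, so at least 48% would stop short. If the post-training survey opened only on full completion, these shares would give no rating. If it opens to partial viewers, the loss is much smaller. The documents do not say which applies.

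**3. Effect on the mean rating.** Let q be the share of the arm without a rating and d the amount, in SD, by which they would have scored lower. The full-arm mean is (1 − q) × m + q × (m − d) = m − q × d, where m is the raters' mean, so the raters-only mean is too high by q × d. Both q and d are assumptions. The 42% is the planning figure for loss at six months, borrowed as an upper illustration. The 10% and 27% have no source in the documents.

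| q | d = 0.5 SD | d = 1.0 SD |
|---|---|---|
| 10% | 0.05 | 0.10 |
| 27% | 0.14 (0.135) | 0.27 |
| 42% | 0.21 | 0.42 |

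For scale, the 95% half-width of the raters-only mean, t/√n in SD units, is 0.21 with 90 raters (q = 10%) and 0.26 with 58 raters (q = 42%), starting from 100. The bias is minor beside sampling error at q = 10% and can exceed it at q = 42%.

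**4. Interviews.** As an illustration, treat the 15 as random draws and assume 30% of the arm stopped early. If stoppers accept at r times the rate of others, their share among interviewees is 0.3r/(0.3r + 0.7).

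| r | Share | Expected of 15 | Chance of none |
|---|---|---|---|
| 1 | 30% | 4.5 | 0.7¹⁵ = 0.5% |
| 1/4 | 9.7% | 1.5 | 22% |
| 1/10 | 4.1% | 0.6 | 53% |

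Without completion as a characteristic, hearing from stoppers depends on their uptake, which the documents do not give. Actual sampling is purposive, so these figures show only the direction and rough size.

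**The case against.** The strongest reply is that silence is not exclusion. No text limits the post-training survey to finishers, and step 3.3 carries no completion condition. The survey appendix is not part of the material available, and reminders are planned for incomplete follow-up. Interviewees are drawn from everyone assigned to the intervention, and the strategy aims at differing perspectives. Completion is itself an acceptability measure, does not depend on answering a survey, and carries the only acceptability hypothesis. Table 2 also reports survey completion at the post-training point, so non-response will be visible.

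Most of this stands, and it rules out some stronger readings:

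- A reader might infer that acceptability as a whole is judged almost only by stayers. It is not: completion counts those who left.
- A reader might infer that early stoppers give no rating. The plan leaves their route unstated; it does not bar them.
- A reader might infer that choosing interviewees by gatekeeper behaviours favours month-1 survey responders. The sampling paragraph does not say which measurement is meant, and Table 2 also collects this measure at baseline and directly after the training.
- A reader might take 27% non-rating from the planned mean of 73%. That mean is a percentage of time spent on the training, not a share of people who answer a survey.

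What the reply does not remove is that completion shows how many stopped, not why, and cannot correct a CSQ-8 or SUS mean. Its own denominator also needs settling. Sample Size Considerations takes 100 as the intervention half of 200 participants, while Number of Participants has 200 enrolled per arm and 100 analysed after 50% loss. On the second reading completion too could be computed only in those retained, so the two sections must be reconciled.

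**Conclusion.** The point holds for the opinion-based part of acceptability: satisfaction, usability and interviews. As written, the plan has no step that obtains ratings from people who stop early and no sampling rule that seeks them for interview, so these data will probably lean toward those who stayed. Under the assumed score gap of 0.5 to 1.0 SD, the overstatement of the mean runs from 0.05 SD (q = 10%) to 0.42 SD (q = 42%). The true size is unknown because the documents give neither the non-response rate nor the gap.

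This does not undermine Hypothesis 2, and no stated figure changes. Nor do the documents support presenting the share satisfied among all randomised as the acceptability result. They define no cut-off for being satisfied, and people who never opened the training cannot rate it. Counting non-raters as not satisfied is at most a labelled lower bound. The gap is modest and cheap to close.

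**What to change.** 1. In Qualitative Interview Sample Considerations, add training completion (finished or stopped early, from the website data already collected) to the maximum-variation characteristics. Keep 15 interviews.
2. In Table 2 and step 3.3, state that the post-training satisfaction and usability items go, with the reminders already planned, to every participant who opened the training, whether or not they finished. Contact details are collected at step 2.5, before the training, so stoppers can be reached. Do not require ratings from people who never opened it.
3. Report CSQ-8 and SUS with the number rating out of the number randomised to S.A.V.E., by completion level. If non-raters are ever counted as not satisfied, define the cut-off in advance and label the result a lower bound.

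The cost is minor REDCap set-up, a fifth characteristic to balance across only 15 interviews, and ratings that may come out less favourable.

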Self-Efficacy: A four-item scale we have previously used to assess confidence to use gatekeeper skills. This scale has shown adequate internal reliability in our prior trial of gatekeeper training.¹⁵

Social Norms: A two-item scale we have previously used that assesses the degree to which one believes that most people do seek (descriptive norm) or should seek (injunctive norm) professional care if having suicidal thoughts. Items show adequate internal reliability.^{14, 48}

Gatekeeper Behaviors: Three items that assess actual self-reported frequency of: 1) recognizing gatekeeper opportunities ("In the last month, how many people have you encountered that you suspected were in an emotional crisis?"); 2) inquiring about suicidal ideation ("...how many times did you directly ask such a person if they were having suicidal thoughts?"); and 3) making a professional referral ("...how many times did you directly refer such a person to mental health or other professional treatment?"). Items are derived from outcome measures in prior gatekeeper training trials.⁶³

Suicidal Ideation: The Depression Symptom Index Suicidality Subscale (DSI-SS) is a four-item measure of suicidal ideation over the past two weeks with strong psychometric properties.^{64, 65}

Help-Seeking: The Actual Help-Seeking Questionnaire (AHSQ) consists of four dichotomous items asking whether in the last month the respondent has sought help for a mental health problem.⁶⁶

Social Support: The Patient-Reported Outcomes Measurement Information System (PROMIS) short form – Emotional Support 4a is a four-item measure of emotional support.⁶⁷

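### The general Cronbach's alpha rule covers three gatekeeper-behavior counts that share a structural zero, so their alpha can look acceptable with no real association between the items

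*Combined protocol and SAP*

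**What the plan says.** The Statistical Analyses section sets one reliability rule for all measures: "For variables measured with multiple items, Cronbach's alpha will be conducted to examine internal reliability". It adds that "when necessary, measurement modifications will be made to improve reliability". It names no exception and no threshold.

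Under Measures, Gatekeeper Behaviors are introduced as "Three items that assess actual self-reported frequency of: 1) recognizing gatekeeper opportunities", followed by asking about suicidal thoughts and by professional referral. Item 1 asks "In the last month, how many people have you encountered that you suspected were in an emotional crisis". Item 2 asks "how many times did you directly ask such a person if they were having suicidal thoughts", and item 3 has the same form for referral. Items 2 and 3 both refer back to the people counted in item 1. The section calls these items, not a scale, and gives no scoring rule.

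Table 2 lists "Gatekeeper behaviors; suicidal ideation; help-seeking, social support" at baseline, post-training and all six monthly follow-ups, with measurement characteristics as their main function. The third key deliverable is the measurement properties of the main outcome variables, to be used in designing the larger trial.

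**The concern.** Alpha is meant for items that are parallel indicators of one trait. Here item 1 counts opportunities, and items 2 and 3 count acts that are possible only when there was an opportunity. Eligibility requires weekly contact with a Veteran, not contact with someone in crisis, so zeros on item 1 are to be expected in some number. Everyone with a zero on item 1 has zeros on all three, and that block of shared zeros creates inter-item covariance by itself.

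The resulting alpha responds to how many respondents had no encounter and how often the others acted. Neither is a property of item coherence. A high value could be read as evidence that the three counts belong together. A low value would, under the plan's own rule, invite changes to the measure in pursuit of a statistic that does not suit it. Either way, a result meant to guide outcome choice in the larger trial would be hard to interpret, and a lack of opportunity would not be separated from a failure to act.

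**Working it through.** The documents state no expected alpha, zero rate or count distribution for these items, so there is no planned figure to reproduce. All rates below are assumptions.

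**Inputs**
- k = 3 items (Measures, Gatekeeper Behaviors).
- u = share answering 0 on item 1: assumed 40% to 80%.
- Item 1 among respondents with an encounter: 1 + Poisson(0.8), so mean 1.8 and variance 0.8 (assumed).
- Items 2 and 3 among the same respondents: independent Poisson with mean λ, from 0.1 to 2 (assumed).
- Items 2 and 3 are recorded as 0, not skipped, when item 1 is 0. The survey itself (Appendix B) is not in the text reviewed.

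**Formula**

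Alpha = k/(k − 1) × (1 − sum of item variances / variance of the sum) = 1.5 × C/(V + C). V is the sum of the item variances and C is twice the sum of the covariances. After a common factor (1 − u) is cancelled:
- V = 0.8 + 3.24u + 2(λ + uλ²)
- C = 2(2 × 1.8uλ + uλ²) = 7.2uλ + 2uλ²

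With u = 0, C = 0 and alpha = 0. The items were set independent among those with an encounter, so any alpha above zero comes from the shared zero alone.

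**Two worked values at u = 0.6**
- λ = 1: C = 4.32 + 1.20 = 5.52; V = 0.8 + 1.944 + 3.2 = 5.944; alpha = 1.5 × 5.52/11.464 = 0.72.
- λ = 0.3: C = 1.296 + 0.108 = 1.404; V = 0.8 + 1.944 + 0.708 = 3.452; alpha = 1.5 × 1.404/4.856 = 0.43.

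**Range**

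| Mean asks or referrals (λ) | 40% zeros | 60% zeros | 80% zeros | Encounter only |
|---|---|---|---|---|
| 0.1 | 0.17 | 0.20 | 0.21 | 0.00 |
| 0.3 | 0.38 | 0.43 | 0.47 | 0.00 |
| 0.5 | 0.50 | 0.57 | 0.61 | 0.00 |
| 1 | 0.64 | 0.72 | 0.77 | 0.00 |
| 2 | 0.74 | 0.81 | 0.85 | 0.00 |

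Simulation gives the same values. In a variant with item 1 as 1 + Poisson(1), n = 200, 70% zeros and λ = 1, the 95% sampling range is 0.66 to 0.81. In the same variant with only 10% zeros, alpha is 0.17 to 0.51 for λ from 0.3 to 4.

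**Second model, with real dependence**

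Let each person encountered be asked, and be referred, with fixed probabilities, independently of each other. With a mean of 2 or 4 people per respondent with an encounter, 30% to 80% zeros and probabilities from 0.1 to 0.7, alpha is 0.35 to 0.90 among those with an encounter and 0.39 to 0.97 overall. For example, with 50% zeros, a mean of 2 people and both probabilities at 0.3, it is 0.61 and 0.73.

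**The case against.** The strongest reply is that the plan never treats these counts as a scale. It uses that word for self-efficacy, social norms and intentions, but not here. Alpha reaches the counts only through a general sentence, which the authors may not have meant to cover three separate counts. A high alpha triggers no action in the plan; only a low one does. The descriptive distributions planned at each timepoint would show the zeros. All of this stands as a limit on the harm, but the sentence as written makes no exception, and no summary restricted to respondents with an encounter is planned.

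A reader might infer more than the documents support:
- *That alpha will look good.* This needs zero and act rates that the documents do not give. With a mean of 0.5 asks or referrals or fewer, alpha stays below the customary 0.70 throughout the table.
- *That the true alpha among those with an encounter is zero.* The 0.00 follows from the assumed independence. The second model gives substantial alpha in that group, with the structural zero adding only part of the total.
- *That the two-item social norms scale has the same fault.* It has no structural zero, and few items lower alpha: at an inter-item correlation of 0.3, alpha is 2(0.3)/1.3 = 0.46 for two items and 8(0.3)/(1 + 7 × 0.3) = 0.77 for eight. The Spearman-Brown coefficient for two items equals standardized alpha, so substituting it would change little.
- *That the items will be summed.* No sum score appears in the documents.

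**Conclusion.** The point holds in limited form. Read literally, the reliability rule covers three counts for which alpha is not a sound index, because it confounds a shared structural zero with any real association. Under independence among those with an encounter and 40% to 80% zeros, alpha runs from 0.17 to 0.85, depending mainly on how often people ask and refer. It can therefore pass as acceptable, or prompt a modification, for reasons unrelated to whether the items cohere. These figures rest on assumed rates and on zeros being recorded instead of skipped.

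Severity is minor. Hypotheses 1.1 to 1.3 and 2 and the sample-size calculations do not use alpha. What is affected is the measurement deliverable for the larger trial.

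**What to change.** In Statistical Analyses, exempt the gatekeeper-behavior counts from the alpha and modification rule. Report the three items separately at each timepoint, combined and by arm:
- the share with at least one encounter;
- asking and referring among all respondents;
- asking and referring among those with at least one encounter;
- count dispersion (for example, a negative binomial estimate) for sizing the larger trial.

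Also state whether items 2 and 3 are skipped or recorded as 0 when item 1 is 0.

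The analysis change needs SAP wording and a few more descriptive tables, with no new data. The conditional summaries will rest on smaller numbers. With 200 respondents and 40% to 80% zeros, they would use 200 × 0.6 = 120 down to 200 × 0.2 = 40 people, and half that (60 down to 20) if loss to follow-up reached 50%.
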